Study Title: One In Seven Gestational Diabetes Study
Sponsor: Prenome
Protocol Number: PRE001/OM001
IRB Submission Number: Pro00049373
Principal Investigator: [name]
Email: [contact]
[contact]
Address: [name]

GESTATIONAL DIABETES GENETIC AND SOCIOECONOMIC RISK PROTOCOL

VERSION DATE: 05/05/2021

STUDY SUMMARY

Investigational Agent(s) (Drugs or Devices)	N/A
IND / IDE / HDE #	No
Special Population(s)	Pregnant Women
Sample Size	10,000 Participants
Funding Source	Prenome (Industry)
Indicate the type of consent to be obtained	Electronic Consent Written Consent
Site	[name]
Research Related Radiation Exposure	Yes No 
DSMB / DMC / IDMC	Yes  No

OBJECTIVES

The objective of the **Gestational Diabetes Genetic Socioeconomic Risk Study** is to generate genome wide association study data (GWAS) to calculate polygenic risk scores (PRS) for the development of gestational diabetes in pregnant women. Prenome's GWAS study will be conducted by collecting DNA samples alongside medical and socioeconomic data and applying data science methodology to generate a polygenic risk score algorithm for gestational diabetes. Our hypothesis is that key genetic variants linked to gestational diabetes will be identified, and sociodemographic characteristics may impact epigenetic factors which further contribute to this risk of gestational diabetes. The PRS generated through our study will be combined with an analysis of epigenetic factors to produce a new method for predicting risk of developing gestational diabetes during pregnancy.

BACKGROUND

Gestational diabetes is a condition where high blood glucose levels occur during pregnancy and the mother was not diabetic before pregnancy. Between 6-9% of pregnancies are affected by this disorder. Gestational diabetes is usually diagnosed with a glucose challenge test where a blood glucose level of 190mg/dL or above would be indicative of gestational diabetes. This test usually occurs around 24-28 weeks into pregnancy. If a patient has other risk factors such as obesity or family history of diabetes, the assessment may be performed earlier.

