The end point of this study is the generation of a polygenic risk score for gestational diabetes from whole genome sequencing of 10,000 DNA samples and sociodemographic data from currently pregnant or recently (< 1 year since birth) pregnant participants.

[figure not shown]
STUDY INTERVENTION

This study does not require any intervention procedures. Participants will be recruited for saliva samples for DNA isolation and data collection only.

PROCEDURES INVOLVED

In order to generate a polygenic risk score for gestational diabetes, Prenome will conduct a GWAS by gathering DNA samples and information from 10,000

Study Title: One In Seven Gestational Diabetes Study
Sponsor: Prenome
Protocol Number: PRE001/OM001
IRB Submission Number: Pro00049373
Principal Investigator: [name]
Email: [contact]
[contact]
Address: [name]

participants who satisfy one of the following qualifications: women who are currently > 24 weeks pregnant, women who have been pregnant within the last year, women with or without a history of gestational diabetes, and women who currently have gestational diabetes.

Participants will be recruited through OB/GYN clinics, patient recruitment organizations or directly by Prenome through an established waitlist and an online advertising campaign. Interested persons will receive materials fully explaining the study and consent processes in detail through a series of pre-prepared email templates. This will include a video, a detailed description in the consent form, and information displayed on the company or study websites (www.prenome.com or www.gestationaldiabetestudy.com). All interested persons will have the option to consult Prenome staff about this study by contacting the [contact] email. This information will be presented online and in communication emails. Prenome will be accessing participant's personal information through medical records to collect information on impactful risk factors and pregnancy outcome data. Samples will be collected from two participant cohorts: a control group containing 5000 participants with normoglycemic pregnancies and a second group containing 5000 diagnosed with gestational diabetes.

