The control cohort will include 5000 adult women who are over 24 weeks pregnant or have given birth to a child within 1 year, who have not received a diagnosis of gestational diabetes and were not diabetic during or before their pregnancy. The diabetic cohort will include 5000 adult women who are over 24 weeks pregnant or have given birth to a child within 1 year, who received any diagnosis of gestational diabetes during their pregnancy. There is no adult age, race or ethnicity exclusion criteria for this study, as our intention is to generate PRS based on diverse populations in line with percentage diversity of the US population. However, minors are not eligible to participate in this study. Male participation is excluded from this

Study Title: One In Seven Gestational Diabetes Study
Sponsor: Prenome
Protocol Number: PRE001/OM001
IRB Submission Number: Pro00049373
Principal Investigator: [name]
Email: [contact]
[contact]
Address: [name]

study. Non-english speakers are excluded from recruitment, this is due to the consent process being available in English only.

VULNERABLE POPULATIONS

Vulnerable populations include pregnant women, visually impaired participants, and women with a history of gestational diabetes. No conversations or documentation given to participants will discuss pregnancy termination. Information produced in this study will be returned to participants, and will not be used to influence decisions related to termination of pregnancy. No inducements, monetary or otherwise will be offered to influence pregnancy termination. In order to ensure the safety and comfort of these participants, the collection kit aims to be as minimally invasive as possible and available to participants in their homes to reduce Covid-19 exposure in clinical environments. Visually impaired persons will have access to this study, and the instructions will be available in a verbal format to increase understanding.

RECRUITMENT METHODS

Participants will be recruited through two channels. The first is through partnered clinical sites referred to Prenome by healthcare providers, where participants receive obstetric care. Clinicians at these sites will be able to identify qualifying participants and register them through the company or study websites (www.prenome.com or www.gestationaldiabetesstudy.com) which are connected to a HIPAA compliant CRM portal, and initiate their study involvement.

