Participants will also be able to directly sign up to this study through a clinical study sign up form featured on the Prenome or study websites (www.prenome.com or www.gestationaldiabetesstudy.com). Any person currently over 24 weeks pregnant or previously pregnant within the last year may register interest in participation on the Prenome website. Prenome will use a series of standardized email templates to communicate with participants at every stage of the study including sign up, consent and kit collection. Interested persons will have access to a video and written materials explaining the study

Study Title: One In Seven Gestational Diabetes Study
Sponsor: Prenome
Protocol Number: PRE001/OM001
IRB Submission Number: Pro00049373
Principal Investigator: [name]
Email: [contact]
[contact]
Address: [name]

and consent processes in detail. They will then be able to complete the sign-up and consent process online. Participants may request a consultation with Prenome to discuss the study if they require more information. Information about study participation through this route will be advertised online including social media and pregnancy related blogs. External sites will be given access to the same advertising materials for recruitment.

COMPENSATION FOR PARTICIPATION IN RESEARCH ACTIVITIES

All participants will receive a \$20 Uber Eats or Amazon gift card, upon delivery of their saliva sample to the Prenome lead site, for contributing to this research study. The gift card will be emailed to participants by default, but participants may request a physical gift card be mailed to them.

WITHDRAWAL OF PARTICIPANTS

Participants may withdraw from the study at any stage of the process. In order to formally withdraw, participants can request a withdrawal form through the Prenome contact email ([contact]) supplied in their communication emails, consent form, collection kit or on the Prenome website. Participants can physically or digitally sign the withdrawal form, and return this to the contact email address or Prenomes mailing address. Upon receiving the withdrawal request, all sequencing, medical and sociodemographic data tied to the participant ID will be removed from the Prenome database and CRM. All saliva, DNA and library samples tied to that participant will be removed from storage and destroyed immediately.

RISKS TO PARTICIPANTS

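### The protocol states conflicting entry rules, and its control definition rests on absence of a diagnosis, so women not yet tested for gestational diabetes can be counted as controls

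*Protocol*

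**What the plan says.** Eligibility is described in four places in the protocol.

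- **STUDY ENDPOINTS:** the score is to be built from "currently pregnant or recently (< 1 year since birth) pregnant participants".
- **PROCEDURES INVOLVED:** recruitment is of "participants who satisfy one of the following qualifications: women who are currently > 24 weeks pregnant", followed by "women who have been pregnant within the last year, women with or without a history of gestational diabetes" and, last, women who have gestational diabetes now. The same section then describes the control group as 5,000 women with normoglycemic pregnancies.
- **INCLUSION AND EXCLUSION CRITERIA:** each cohort is "5000 adult women who are over 24 weeks pregnant or have given birth to a child within 1 year". Controls must have had no diagnosis of gestational diabetes and no diabetes during or before the pregnancy. Cases must have had a diagnosis during their pregnancy.
- **RECRUITMENT METHODS:** "Any person currently over 24 weeks pregnant or previously pregnant within the last year may register interest in participation" on the website.

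Two other statements bear on the point. BACKGROUND says of the glucose test: "This test usually occurs around 24-28 weeks into pregnancy". SHARING RESULTS WITH PARTICIPANTS treats each woman's pregnancy outcome as settled when her sample is taken.

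**The concern.** In a case-control GWAS the cohort label is the outcome. If the protocol has several entry rules in print, the clinical sites that register participants and the online sign-up form may apply different ones. If control status needs only the absence of a diagnosis, a woman who has not been tested is indistinguishable from one who tested negative.

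Some untested women will be latent cases. Mixing them into the controls pulls the control allele frequencies toward those of the cases, shrinks the estimated allele effects toward the null, and weakens the score built from them, which is the study's only endpoint. If no test result or completed window is recorded at assignment, these women are hard to identify later.

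**Working it through.** **Step 1. The rules side by side**

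| Place | Connector | Recency | Gestational diabetes status |
|---|---|---|---|
| STUDY ENDPOINTS | – | Currently pregnant, or less than 1 year since birth | – |
| PROCEDURES INVOLVED, list | Any one item | Over 24 weeks, or pregnant in the last year | History or no history |
| INCLUSION AND EXCLUSION CRITERIA | All conditions | Over 24 weeks, or birth within 1 year | Controls: no diagnosis, no time frame. Cases: diagnosis during the pregnancy |
| RECRUITMENT METHODS | – | Over 24 weeks, or pregnant in the last year (registering interest) | – |

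Three things follow.

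1. The list asks for "participants who satisfy one of the following qualifications". Having or not having a history is true of every woman, so as written the list excludes no woman.
2. A pregnancy in the last year that ended without a birth, possibly before 24-28 weeks, meets the list and the sign-up wording. It fails the formal requirement to "have given birth to a child within 1 year".
3. The formal criteria themselves admit a woman just past 24 weeks, without a diagnosis and not yet tested, as a control. This is the main route to untested controls, and it stays open even if the list is repaired. It sits badly with the normoglycemic description and with the claim that outcomes are settled at sampling.

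**Step 2. The plan's own figure**

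5,000 + 5,000 = 10,000, which agrees with the stated sample size. The protocol gives no alpha, power or effect size, so there is no power figure to reproduce.

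**Step 3. Number of latent cases among controls**

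Inputs: 5,000 controls (PROCEDURES INVOLVED), prevalence 6-9% (BACKGROUND), and untested share u, which is assumed. Untested women are taken to carry the protocol's average prevalence.

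Contamination c = u × prevalence; latent cases = 5,000 × c.

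- u = 5%, prevalence 6%: c = 0.05 × 0.06 = 0.3%, or 15 women.
- u = 20%, prevalence 9%: c = 0.20 × 0.09 = 1.8%, or 90 women.
- u = 100% (upper bound): c = 6-9%, or 300-450 women.

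**Step 4. Effect on power**

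The case-control difference in allele frequency shrinks by the factor (1 − c), and the non-centrality of the test by about (1 − c)².

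Illustration, all assumed: control allele frequency 0.30, odds ratio 1.21, two-sided alpha 5e-8, 10,000 alleles per group. The case odds are (0.30/0.70) × 1.21 = 0.5186, so the case frequency is 0.5186/1.5186 = 0.3415. The contaminated control frequency is (1 − c) × 0.30 + c × 0.3415.

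| c | (1 − c)² | Power |
|---|---|---|
| 0 | 1.000 | 80% |
| 0.3% | 0.994 | 79% |
| 1.8% | 0.964 | 76% |
| 6% (all untested) | 0.884 | 67% |
| 9% (all untested) | 0.828 | 60% |

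**The case against.** The strongest reply is that INCLUSION AND EXCLUSION CRITERIA is the formal eligibility section and the list in PROCEDURES INVOLVED is narrative about the pooled recruitment population. A woman admitted only by the loose list fits neither formal cohort. RECRUITMENT METHODS covers only registering interest, not enrolment, and the sponsor plans to read medical records for pregnancy outcomes.

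Most of this stands. A reader might infer that every woman is eligible; the formal criteria do not allow that. But the protocol does not say which section governs, and sites and the web form can work from either text. The reply also leaves untouched the untested woman just past 24 weeks, because she meets the formal control rule.

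A reader might also infer that women with gestational diabetes in an earlier pregnancy can enter as controls. The documents do not support that. The control rule bars a diagnosis without any time limit, and read plainly it excludes them. What remains is an ambiguity: the case rule is tied to the pregnancy, the control rule names no pregnancy, and the list welcomes women with a history. On the plain reading, a woman with earlier disease and a normal recent pregnancy is invited by the list but belongs to neither cohort.

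On size, the reply is right that the upper bound is not realistic. Women past 28 weeks or already delivered would usually have passed the test window.

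**Conclusion.** The point holds as an internal contradiction with a modest likely effect. The entry list restricts nothing, the recency windows conflict, and the control rule does not secure the normoglycemic status that the protocol claims for controls. It should be corrected, but it does not undermine the design.

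On the assumption that 5-20% of controls are untested, 15-90 of 5,000 (0.3-1.8%) are latent cases and illustrative power falls from 80% to about 79-76%. This rests on the protocol's 6-9% applying to untested women, and on an odds ratio, allele frequency and alpha that are not in the protocol.

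Two larger figures should not be taken as the expected effect. The count of 300-450 latent cases needs every control to be untested. A fall to 76-70% would follow if 2-5% of controls were full cases through earlier gestational diabetes, but that share is not in the documents and the formal criteria, read plainly, exclude those women.

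**What to change.** 1. In PROCEDURES INVOLVED, replace the list with a reference to INCLUSION AND EXCLUSION CRITERIA as the sole eligibility rule.
2. In PROCEDURES INVOLVED and RECRUITMENT METHODS, and on the sign-up form, replace the window of any pregnancy in the last year with a birth within 1 year.
3. In INCLUSION AND EXCLUSION CRITERIA, state that controls have no diagnosis of gestational diabetes in this or any earlier pregnancy.
4. In the same section, count a woman as a control only once her medical record shows a negative routine test, or a completed 24-28 week test window without a diagnosis. PROCEDURES INVOLVED already provides for access to the record, so no extra testing is asked of participants.

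The cost is wording in three sections and on the sign-up form, a check in a record that is already to be read, and some would-be controls deferred until the window has passed or turned away. It is best done before enrolment.

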Registered participants may request collection kits to be sent directly to a desired address (personal or clinical recruitment site) and may consent to participate electronically; this is to address safety concerns due to COVID-19. Once recruited into the study, participants will be mailed a DNA sample collection kit (provided by Prenome) containing either an Oragene OGD-510 or OCD-100 saliva tube or Zymo R1210-E saliva tube. These sample collection devices have received FDA 510(k) clearance, and contain chemistry which lyses enveloped viruses such as SARS-CoV2, ensuring subject safety. Participants will register the identifier barcode on the collection device, which will be used to link medical data to their sample. The participant will spit directly into the saliva collection tube for DNA sample collection, and subjects will be asked to complete a questionnaire about socioeconomic demographics and medical history. Access to this questionnaire will

Study Title: One In Seven Gestational Diabetes Study
Sponsor: Prenome
Protocol Number: PRE001/OM001
IRB Submission Number: Pro00049373
Principal Investigator: [name]
Email: [contact]
[contact]
Address: [name]

be granted online at the point of sample collection kit registration. This questionnaire will take no more than 30 minutes to complete.

Regardless of the recruitment site, samples will be returned to the Prenome study lead site for processing, DNA sequencing, and data analysis. Research scientists handling participant samples will have access to the unique identifier number on the collection device ONLY. This is to ensure participant privacy and protection of PHI, while also allowing processing to remain blind to participants' diabetic status.

The samples will undergo DNA isolation and library preparation following the DNA/RNA Prep Work Flow with Exome Enrichment using Illumina preparation chemistry. Whole genome and whole exome sequencing will be carried out, sequencing all samples to a minimum coverage of 1X. The sequencing data will be used to identify linkage of associated alleles and variants that determine risk of gestational diabetes, and then tied to medical or socioeconomic data which increases or decreases risk.

This clinical study will result in a novel PRS which can be used to assess risk of gestational diabetes. Any remaining isolated DNA or saliva will be stored in the Prenome BioBank using the de-identified barcode assigned at collection.

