Once data has passed quality control, the reads generated will be aligned to reference genomes, using illumina's basespace platform to produce BAM files containing aligned reads which can be linked to the index barcodes for each participant. The participant data will be linked to the sequencing data using the individual barcode assigned at sample collection. This data will not contain names or full addresses of participants but will contain medical information and sociodemographic survey information. We will combine the study sequencing data with public genetic datasets (UKBioBank, BioBank Japan) which contain information on pregnant women. This information will be analysed for specific alleles and gene variants that can be linked to gestational diabetes using Python to identify GWAS data. The GWAS data will then be run through a variety of PRS algorithms using Python for Prenome's proprietary algorithm and Allelica for publicly available PRS algorithms.

Study Title: One In Seven Gestational Diabetes Study
Sponsor: Prenome
Protocol Number: PRE001/OM001
IRB Submission Number: Pro00049373
Principal Investigator: [name]
Email: [contact]
[contact]
Address: [name]

DATA MANAGEMENT AND CONFIDENTIALITY

All sequencing data from participant samples will be generated on the NovaSeq 6000. Sequenced data will be transferred from sequencing equipment to password protected cloud storage. This information will be anonymised and catalogued using unique identifiers to protect confidentiality. Genome sequencing data will be checked for quality control management, and then reads will be filtered and aligned to a reference genome.

These aligned reads will be matched to participant medical records, used to generate GWAS data and identify linkage of associated alleles or gene variants which can be correlated with gestational diabetes. This data may be combined with publicly available whole genome sequencing data such as the UKBiobank and Biobank Japan. Once variants have been detected, polygenic risk scores will be generated using publically available algorithms and Prenome's internal algorithms. These scores will be tied to sociodemographic risk factors, generated from the study questionnaire, to calculate a complete risk score composed of genetic and epigenetic factors. All data outcomes and statistical analyses produced by this study will be reviewed by a data monitoring committee (DMC).

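### The objective and the final score claim an epigenetic component, but nothing the protocol describes measures one

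*Protocol*

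**What the plan says.** Three statements in the body of the protocol bring in epigenetics.

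- **Objectives, hypothesis:** "sociodemographic characteristics may impact epigenetic factors which further contribute to this risk of gestational diabetes".
- **Objectives, deliverable:** "The PRS generated through our study will be combined with an analysis of epigenetic factors to produce a new method for predicting risk".
- **Data Management and Confidentiality, final score:** the polygenic scores are to be tied to "sociodemographic risk factors, generated from the study questionnaire, to calculate a complete risk score composed of genetic and epigenetic factors".

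The remaining sections describe a different set of inputs.

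- **Study Endpoints** gives one endpoint: "the generation of a polygenic risk score for gestational diabetes from whole genome sequencing of 10,000 DNA samples and sociodemographic data".
- **Study Intervention** limits what is taken from participants: "Participants will be recruited for saliva samples for DNA isolation and data collection only".
- **Procedures Involved** describes the laboratory work: "Whole genome and whole exome sequencing will be carried out, sequencing all samples to a minimum coverage of 1X". The variants found are to be used to determine risk, "and then tied to medical or socioeconomic data which increases or decreases risk". It also provides for a participant questionnaire and for access to participants' information "through medical records to collect information on impactful risk factors and pregnancy outcome data".
- **Data Analysis** adds public genetic datasets from two biobanks.

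**The concern.** The objective names a component for which the study appears to collect no data. The hypothesis is also a statement about a pathway: social circumstances affect epigenetic factors, and these add to the risk of gestational diabetes. Testing that requires the intermediate to be measured. An association between questionnaire answers and gestational diabetes, however strong, says nothing about whether it runs through an epigenetic mark.

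The label matters beyond the protocol. The sponsor plans open-access publication and expects the results to lead to a predictive test. A score presented as genetic and epigenetic, but built from variants plus sociodemographic and medical data, would tell readers and users that it has a property it does not have.

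**Working it through.** The protocol gives no figure to reproduce here, and no sample-size or error-rate formula applies. The check compares what is promised with what is collected.

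**1. Count the promises.** The word *epigenetic* (or *epigenetics*) occurs 4 times in the protocol: twice in Objectives, once in Data Management and Confidentiality, and once in the title of a cited reference. That leaves 4 − 1 = 3 uses in the body text, which are the three statements quoted above.

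**2. List the inputs and ask what each yields.**

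| Data source | Where described | What it is said to yield | Epigenetic measurement described? |
|---|---|---|---|
| Sequencing of saliva DNA | Procedures Involved; Data Analysis | Alleles and gene variants | No |
| Questionnaire | Procedures Involved; Protected Health Information | Socioeconomic and medical-history items | No |
| Medical records | Procedures Involved; Protected Health Information | Risk factors, health data, pregnancy outcomes | No |
| Public biobank data | Data Analysis; Data Management and Confidentiality | Genetic and whole genome sequence data | No |

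Result: 0 of 4 sources.

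**3. Look for a measurement under another name.** The terms methylation, bisulfite, histone and chromatin occur 0 times. The laboratory workflow has RNA in its name, but the text describes only DNA isolation and genome and exome sequencing, with no RNA output. The withdrawal section, which says what is erased when a participant leaves, names sequencing, medical and sociodemographic data and no further class. Saliva and DNA are banked for 10 years, so a later assay is conceivable, but none is planned.

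**4. Try the reading in which *epigenetic* means *non-genetic*.** The sentence on the final score points that way, since questionnaire factors are the only thing it adds to the polygenic score. Put beside the hypothesis, this reading fails. There, sociodemographic characteristics act on epigenetic factors, so one is the cause and the other the intermediate.

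- If the two terms mean the same, the hypothesis is circular.
- If they differ, the intermediate is never measured, and the final-score sentence calls the cause by the name of the intermediate.

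The protocol is inconsistent on either reading.

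**5. Compare with the endpoint.** The endpoint needs sequencing and sociodemographic data only, and both are collected. Endpoints affected: 0 of 1.

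**The case against.** The strongest reply is that this is loose vocabulary and no analysis has been lost. The final-score sentence, the endpoint, the Background rationale and the Procedures all describe the same plan, genetic data combined with non-genetic risk factors, and every one of those inputs is collected. On that view the intended analysis can be run and is only misnamed. It can be added that the hypothesis is conditional and commits the sponsor to no assay, so that only two statements truly promise epigenetic content. Finally, a finding of absence rests on incomplete material: one figure, the questionnaire and the laboratory procedures are not shown.

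Part of this stands. The sponsor may well have meant non-genetic factors throughout, and nothing here shows that an assay was planned and then forgotten. The count of 0 of 4 describes what the protocol says, and the grouping into four sources is the reviewer's own. The hypothesis may also stay as background if it is marked as untested.

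The rest does not remove the fault. The hypothesis itself separates the two concepts, so the protocol's own usage blocks the charitable reading. A figure could not by itself reconcile the conflicting text. An assay on participants' samples belongs in the protocol's procedures. A statistical analysis plan can define a model, but it cannot supply a variable that nobody measured.

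**Conclusion.** The concern holds. Taken literally, the epigenetic analysis in the objective cannot be carried out with the data described, the epigenetic part of the hypothesis cannot be tested, and the final score is given a name its inputs do not support. Three statements need correcting, and none of the 4 data sources supports them as they stand. The polygenic score, the case and control cohorts and the single endpoint are untouched, so this is a correction that should be made and not a threat to the main analysis. The conclusion assumes that the unshown figure does not introduce an epigenetic assay that the text never mentions.

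**What to change.** First ask the sponsor whether any epigenetic measurement is intended.

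**If none is intended,** make three wording changes:

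1. In Objectives, describe the polygenic score as being combined with sociodemographic and medical (non-genetic) risk factors. This matches the endpoint and the Procedures.
2. In Data Management and Confidentiality, describe the complete score as made up of genetic and non-genetic factors.
3. In the hypothesis, delete the epigenetic clause or mark it as rationale that this study does not test.

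This changes no sample, cohort, data source or scoring step. The price is a narrower scientific claim.

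**If a measurement is intended,** the procedures must name the assay, the variables it yields and how they enter the score. That is no longer a wording change: it adds laboratory work, and its cost cannot be judged from the protocol. Sampling time would also need attention, because participants are enrolled after 24 weeks of pregnancy or within a year of birth, and an epigenetic mark, unlike inherited sequence, need not be the same then as before diagnosis.
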